#### **7.5.1.1 Subgroup Analyses**

Two-year survival rates along with two-sided 80% CI based on the log-log transformation will be presented within subsets defined by information recorded on the baseline CRF.

This summary and comparison based on the unstratified chi-square test will be provided for the following subgroups:

- by age (< 65,  $\geq$  65)
- by gender (male, female)
- by M-Substage at study entry (M1a/M1b, M1c)
- by ECOG performance status (0, 1)

- by baseline LDH ( $\leq$ ULN,  $>$  ULN)
- by baseline LDH ( $\leq 2 \times$  ULN,  $> 2 \times$ ULN)
- by BRAF mutation status (positive, negative, unknown)
- by subtype (acral, cutaneous, other)

In case a subgroup includes less than 10 subjects, the analysis for the given subgroup will not be carried out (or the possibility of combining subgroups will be considered).

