## **7.5 Efficacy**

All hypothesis testing will be two-sided and will be based upon a significance level of 0.20.

No type I error rate multiplicity adjustment will be made for secondary endpoint testing. P-values associated with the comparisons of OS, DCR and PFS will be purely descriptive in nature. All efficacy analyses will be based on all randomized subjects, as randomized, unless indicated.

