### **7.5.2.2 Subgroup Analyses**

OS will be summarized within subsets defined by information recorded on the baseline CRF (with two-sided 80% CI for the median OS calculated via the method of Brookmeyer and Crowley). For informal comparisons of OS within these subsets, the HR, and its 80% two-sided CI, of ipilimumab

to DTIC will be computed using an unstratified Cox proportional hazards model with treatment as the single covariate.

This summary and comparison will be provided for the following subgroups:

- by age (< 65,  $\geq$  65)
- by gender (male, female)
- by M-Substage at study entry (M1a/M1b, M1c)
- by ECOG performance status (0, 1)
- by baseline LDH ( $\leq$  ULN,  $>$  ULN)
- by baseline LDH ( $\leq 2 \times$  ULN,  $> 2 \times$  ULN)
- by BRAF mutation status (positive, negative, unknown)
- by subtype (acral, cutaneous, other)

In case a subgroup includes less than 10 subjects, the analysis for the given subgroup will not be carried out (or the possibility of combining subgroups will be considered).

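### The 2-year survival subgroup tests (up to 18 levels at two-sided 0.20, no interaction test, no per-arm minimum) cannot show effect modification and are miscalibrated in small levels

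*SAP*

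**What the plan says.** SAP 7.5.1 makes the 2-year survival rate the primary endpoint and compares it with a chi-square statistic built from Kaplan-Meier estimates and Greenwood variances. SAP 7.5.1.1 carries this into subgroups: "This summary and comparison based on the unstratified chi-square test will be provided for the following subgroups". Six factors have two levels (age, gender, M-substage, ECOG, LDH cut at ULN, LDH cut at 2 x ULN). Two have three: "by BRAF mutation status (positive, negative, unknown") and "by subtype (acral, cutaneous, other").

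The level comes from SAP 7.5: "All hypothesis testing will be two-sided and will be based upon a significance level of 0.20". The size rule is: "In case a subgroup includes less than 10 subjects, the analysis for the given subgroup will not be carried out"; the same sentence adds that combining subgroups may be considered instead. It gives no minimum per arm.

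Two cautionary labels appear nearby. SAP 7.5 says: "P-values associated with the comparisons of OS, DCR and PFS will be purely descriptive in nature". SAP 7.5.2.2, on the same eight factors, says: "For informal comparisons of OS within these subsets, the HR, and its 80% two-sided CI". Neither names the 2-year survival subgroup tests. The SAP contains no treatment-by-subgroup interaction test and no rule for reading the subgroup results.

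**The concern.** A p-value within a level asks whether the arms differ in that level. It does not ask whether the treatment effect differs between levels, which is what a subgroup table is normally read for. With many levels tested at 0.20, a mix of significant and non-significant rows will appear whether or not heterogeneity exists. The primary endpoint has less protection here than OS, since its subgroup comparisons carry neither label.

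A second problem is the small levels. A floor on the total says nothing about the smaller DTIC arm. With about 3 DTIC subjects and low 2-year survival, an arm often has no survivors, and a Greenwood-variance statistic then treats that arm as known without error. At stake is how subgroup results for the primary endpoint are reported and read.

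**Working it through.** **Inputs.** From SAP 5: about 180 subjects, 2:1 (120 ipilimumab, 60 DTIC), 2-year survival 25% versus 12.5%, error rate 0.20, power 80%, at least 2 years of follow-up. From SAP 7.5 and 7.5.1.1: two-sided 0.20, the factor list, the floor of 10. Assumed: no censoring before 2 years, so the Greenwood variance is p(1-p)/n; the unstratified test is the SAP 7.5.1 formula with one stratum; subgroup shares, which the documents do not give.

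**The plan's own power.** SE = sqrt(0.125 x 0.875/60 + 0.25 x 0.75/120) = 0.0582. Power = Phi(0.125/0.0582 - 1.2816) = 0.807 by formula, and 0.800 by exact calculation or simulation. The stated 80% is reproduced, so this is the right form of the test.

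**Number of tests.** 6 x 2 + 2 x 3 = 18 at most. BRAF unknown should be nearly empty: Protocol 3.3.2 excludes subjects whose BRAF status the screening test cannot determine, and the SAP 2.2 stratum is yes/no. Without it there are 17.

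**No effect anywhere.** Expected false positives are 18 x 0.20 = 3.6. If the tests were independent, the chance of at least one would be 1 - 0.8^18 = 0.982 (0.977 for 17). They are not independent, because the factors re-divide the same subjects and the LDH cuts are nested. Simulation of 120 versus 60 subjects, with the 10-subject floor, gave:

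| Setting | At least one significant level | Mean number |
|---|---|---|
| Three sets of assumed shares, 20% survival in both arms | 0.937, 0.914, 0.941 | 3.8 to 4.0 |
| Correlation 0, 0.3, 0.6 between factors, 20.83% in both arms | 0.940, 0.936, 0.915 | 4.0 to 4.1 |

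**Uniform effect, 25% versus 12.5% in every level.** At least one factor had a significant level beside a non-significant one in 0.950 to 0.973 of trials (three share sets) and 0.956 to 0.972 (three correlations). The mechanism can be seen by hand. A level holding half the trial (60 versus 30) has exact power 0.61, so a 50/50 factor is discordant with probability 2 x 0.61 x 0.39 = 0.48, with no heterogeneity at all.

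**Small levels, exact binomial calculation, common rate 12.5% to 25%.**

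| Ipilimumab vs DTIC | True size of the 0.20 test | Statistic undefined (zero total variance) |
|---|---|---|
| 7 vs 3 | 0.18 to 0.31 | 6% to 26% |
| 13 vs 7 | 0.25 to 0.27 | 0.3% to 7% |
| 60 vs 30 | 0.22 to 0.23 | 0% |

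The chance that all DTIC subjects have died by 2 years, at a 12.5% rate, is 0.875^3 = 0.67 with 3 subjects and 0.875^7 = 0.39 with 7. Taking that arm's variance as zero, 2 of 7 versus 0 of 3 survivors gives chi-square = (2/7)^2 / [(2/7)(5/7)/7] = 2.80 and p = 0.09, significant at 0.20. Fisher's exact two-sided p for the same table is 1.0.

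**What interaction tests would do.** Eight tests, if independent: 1 - 0.8^8 = 0.83 chance of a false signal at 0.20, and 1 - 0.95^8 = 0.34 at 0.05. Simulated heterogeneity tests at 0.20 gave 0.81 to 0.88.

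**The case against.** Much of the case on the other side stands.

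- No decision, gate or alpha rests on a subgroup. A reader might infer from the 91% to 94% figure that the trial's type I error is inflated; the documents do not support that, since the primary test is a single stratified comparison.
- A reader might take the 67% chance of no DTIC survivors as the chance that the test fails. It is not. The denominator adds both arms' variances, so the statistic is undefined only when both are zero: 6% to 26% at 7 versus 3. The rest is miscalibration, and the range at that size includes a value below 0.20.
- SAP 7.5.1.1 and 7.5.2.2 might be read as contradicting each other. They treat different endpoints with different measures; the difference is one of labelling and presentation.
- Intervals do not remove chance findings. An 80% Wald interval for the difference excludes zero exactly when the unpooled test gives p below 0.20, and OS hazard ratios with 80% intervals carry similar exposure. Interaction tests at 0.20 still give about an 83% chance of a false signal.
- The SAP already allows levels to be combined, though only as a possibility and only below 10 subjects in total. Levels of 10 to 20 subjects are not covered.

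These points limit the consequence. They do not make within-level p-values informative about effect modification, and they do not repair the test at 7 versus 3.

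**Conclusion.** The point holds as a matter of interpretation and small-sample validity. The planned table will almost always contain nominally significant levels under no effect (91% to 94% of trials) and discordant levels under a uniform effect (95% to 97%), so its pattern of p-values says little about heterogeneity. At the permitted minimum, the nominal 0.20 test has a true size of 0.18 to 0.31.

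The simulated figures rest on assumed subgroup shares and correlations, but varied little across those tried. All figures assume no censoring before 2 years and the planned 180 subjects; Protocol 3.1 reports 258 enrolled but does not give the number randomized. The documents do not support a claim that the primary analysis is compromised or that the SAP plans to draw subgroup conclusions.

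**What to change.** In SAP 7.5.1.1:

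1. Remove the within-level p-values, or state that they are descriptive and are not evidence of a difference between subgroups.
2. Show the difference in 2-year survival with its confidence interval for each level.
3. Base any statement about heterogeneity on one treatment-by-factor interaction test per factor, labelled exploratory, with its level stated in advance and the number of tests reported.
4. Set the minimum size per arm, and extend the existing option to combine levels to cases where an arm has too few subjects or no survivors.

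The cost is SAP wording and minor programming; the primary analysis is unchanged. Interaction tests will have low power, and some 80% intervals will still exclude zero by chance. The Protocol synopsis gives a database lock of 03Jun2019, so a change made now should be documented as made after lock; relabelling and re-presenting the table in the report remains possible.

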### **7.5.1.2 Sensitivity Analyses**

The following analyses will be conducted

- An unstratified chi-square test will be performed to compare survival rate at 2 years after randomization between treatment groups
- The stratified and unstratified chi-square tests based on the modified OS accounting for subsequent PD-1/PD-L1 therapy.

## **7.5.2 Overall Survival**

OS within treatment group, estimated using the KM product-limit method, will be plotted. Summary tables will report the median OS together with a two-sided 80% confidence interval (CI) for the median, calculated using the method of Brookmeyer and Crowley. All available events (deaths) in the database will contribute to the analysis of OS.

The extent of follow-up within treatment group, defined as the time between randomization and last known alive date whether status is alive or dead, will be summarized, as will be the currentness of follow-up, defined as the time between last known alive date and data cut-off date (defined by last patient last visit date). Subjects who died and subjects with last known date alive on or after data cut-off date will be considered as current.

- Summary of OS
- Extent of follow-up
- Currentness of follow-up

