#### **4.2.2 Overall Survival**

OS is defined for each subject as the time between randomization date and the date of death (of any cause). If a subject has not died, the subject will be censored at the time of last contact (last known alive date).

A modified variable will be examined for the purposes of sensitivity analysis:

- OS accounting for subsequent PD-1/PD-L1 therapy will be defined through addition of the following restriction to the primary definition: subjects who receive subsequent PD-1/PD-L1 cancer therapy will be censored at the start date of subsequent PD-1/PD-L1 therapy.

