## 7 STATISTICAL ANALYSES

### 7.1 General Methods

No interim analyses are planned for this study. The final analysis will be performed when a minimum of 2 year follow-up is reached by all randomized subjects.

Unless otherwise noted, the bulleted titles in the following subsections describe tabulations of discrete variables, by the frequency and proportion of subjects falling into each category, grouped by treatment (with total). Percentages given in these tables will be rounded to the first decimal and, therefore, may not always sum to 100%. Percentages less than 0.1 will be indicated as ‘< 0.1’. Continuous variables will be summarized by treatment group (with total) using the mean, standard deviation, median, minimum and maximum values. Subject listings will be produced to accompany the tabulations. Time-to-event variables (e.g. time-to resolution) will be analyzed using the Kaplan-Meier technique. When specified, the median will be reported along with 80% CI using Brookmeyer and Crowley method (using log-log transformation for constructing the confidence intervals). The conventions to be used for imputing partial dates for analyses requiring dates are described in [Section 8](#).

Frequency tables of subject characteristics and subset analyses of efficacy endpoints (including those by M-substage and BRAF mutation status) will be based on the assessment recorded on the baseline CRF. However, stratified analyses will be based on the variables used by the IVRS to randomize the subject.

Assessments taken during re-induction and subsequent progression follow-up phase will not contribute to derived endpoints, such as BOR or PFS, since these assessments are necessarily following an initial progression. However exploratory version of these endpoints corresponding to the administration of re-induction therapy may be performed (if there are sufficient data) - details will be provided in the DPP.

All statistical analyses will be carried out using SAS software (SAS Institute, Cary, North Carolina, USA), unless otherwise noted.

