### **7.5.1 Survival Rates at Specified Time Points**

Yearly survival rates will be calculated for each treatment group using the KM product-limit method, along with their corresponding log-log transformed 80% CIs.

Two-year survival rate is the primary endpoint. The survival rate at 2 years will be compared between treatment group using a chi-square test stratified by M substage (M1a+M1b versus M1c) and BRAF mutation status (yes vs no), as recorded in the IVRS. The stratified chi-square test is defined by the following formula:

$$\chi^2 = \frac{\left( \sum_{s=1}^m \hat{S}_{1s}(t) - \hat{S}_{2s}(t) \right)^2}{\sum_{s=1}^m \hat{V}(\hat{S}_{1s}(t)) + \hat{V}(\hat{S}_{2s}(t))},$$

where  $\hat{S}_{ks}(t)$  and  $\hat{V}(\hat{S}_{ks}(t))$  be the Kaplan-Meier estimate and variance based on the Greenwood formula for the  $s$ th stratum in the  $k$ th treatment group at time  $t$ .

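### SAP 7.5.2 and 4.2.2 set no common end date for deaths and last-known-alive dates in OS, so survival rates beyond 2 years can be biased down if late deaths are captured more completely than late survival

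*SAP*

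**What the plan says.** - **Deaths.** SAP 7.5.2: "All available events (deaths) in the database will contribute to the analysis of OS". No date limit is attached.
- **Survivors.** SAP 4.2.2: "If a subject has not died, the subject will be censored at the time of last contact (last known alive date"). No date limit is attached here either.
- **Cut-off.** SAP 7.5.2 refers to the "data cut-off date (defined by last patient last visit date"), but only to define currentness of follow-up. It adds: "Subjects who died and subjects with last known date alive on or after data cut-off date will be considered as current". Alive dates after the cut-off are therefore foreseen.
- **Timing.** SAP 7.1: "The final analysis will be performed when a minimum of 2 year follow-up is reached by all randomized subjects". SAP 5 places the primary analysis about 42 months after the first randomization.
- **Outputs.** SAP 7.5.1: "Yearly survival rates will be calculated for each treatment group using the KM product-limit method". With 42 months of calendar time a 3-year rate can be reported, although only the 1- and 2-year rates are named endpoints (SAP 4.1.1 and 4.2.1). SAP 7.5.2 also plots the OS curve, and SAP 7.5.2.1 calls OS the key secondary efficacy endpoint.
- **Lock.** Protocol 1.2 gives the database lock as 03Jun2019. Neither document gives the date of the last patient's last visit.

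**The concern.** Kaplan-Meier estimation requires that the end of a subject's follow-up does not depend on whether the subject has died. Between the last patient's last visit and lock, the SAP does not secure this. A death that becomes known in that interval enters the OS analysis and extends that subject's follow-up. A living subject's follow-up is extended only if someone records a later contact. If the first happens more reliably than the second, deaths are counted against risk sets that are too small, and the right-hand part of the curve is pulled down.

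The outputs at stake are the tail of the OS curve and any 3-year rate. The primary comparison at 2 years is not at stake.

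**Working it through.** **1. The plan's own figure.** SAP 5 assumes 180 subjects at 2:1 (120 and 60), median OS of 12 and 8 months, and exponential survival. The 2-year rates are 0.5^(24/12) = 25% and 0.5^(24/8) = 12.5%, as stated. SAP 7.5 specifies: "All hypothesis testing will be two-sided and will be based upon a significance level of 0.20", so z = 1.2816. With the unpooled variance, SE = √(0.25×0.75/120 + 0.125×0.875/60) = 0.0582. Power = Φ(0.125/0.0582 − 1.2816) = 80.7%, against the stated 80%. The design inputs reproduce and are used below.

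**2. Which estimates can move.** Let C be a subject's time from randomization to the cut-off. With uniform accrual over 18 months and a cut-off at month 42, C lies between 24 and 42 months. A death after the cut-off has an OS time above C, hence above 24 months, and cannot change the estimate at 24 months.

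**3. Number of deaths involved.** The expected proportion alive at cut-off is (1/18)∫S(t)dt from 24 to 42, with S(t) = 0.5^(t/median). This is 0.155 for ipilimumab (18.6 of 120) and 0.063 for DTIC (3.8 of 60). Deaths in the next L months are these numbers times 1 − 0.5^(L/median). The totals are 1.4, 3.8 and 7.0 for L = 1, 3 and 6.

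**4. Worst case.** Assume all deaths up to C + L are counted and all survivors are censored at C. With λ = ln 2/median, the hazard that Kaplan-Meier sees at t > 24 is

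h(t) = λ S(t) P(C ≥ t − L) / { S(t) P(C ≥ t) + (1/18) ∫ [S(t) − S(c + L)] dc },

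with c running from max(24, t − L) to t. The numerator gains every death within the lag. The denominator gains only those subjects who will die before lock. The estimated 3-year rate is S(24) exp(−∫h) over 24 to 36 months.

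| Lag L (months) | Ipilimumab, true 12.5% | Loss | DTIC, true 4.4% | Loss |
|---|---|---|---|---|
| 1 | 11.8% | 0.7 | 4.1% | 0.4 |
| 3 | 10.7% | 1.8 | 3.5% | 0.9 |
| 6 | 9.8% | 2.7 | 3.2% | 1.2 |

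Simulation with 1,000,000 subjects per arm agrees to within 0.1 point. It leaves the 2-year rates at 25.0% and 12.5%, and medians and 1-year rates unchanged.

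**5. Relaxing the worst case (ipilimumab, L = 1, 3, 6).**
- Deaths and survivors both updated to lock: about 12.5% throughout.
- Half of late deaths and half of survivors updated: 12.4 to 12.5%.
- All deaths and half of survivors updated: losses of about 0.4, 0.8 and 1.1 points.
- Half of late deaths and no survivors updated: 12.1%, 11.5% and 11.0%.

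**6. Survivors last seen before the cut-off.** Suppose the last contact falls 0 to 3 months before the cut-off (an assumption).
- With deaths counted to lock, the ipilimumab 3-year rate is 10.6%, 9.5% and 9.0%, and the 2-year rate is at most 0.1 point low.
- Truncating deaths at the cut-off, with survivors left at last contact, gives about 11.2%. Truncation alone still leaves a loss of about 1.3 points.

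**The case against.** The strongest reply is that the SAP writes no asymmetry. Last contact has no upper limit, and SAP 7.5.2 expects some alive dates on or after the cut-off. A reader might infer that survivors are fixed at the cut-off, and so that late survival rates are biased down as a matter of course. The text does not support that. It leaves both dates open, and the bias needs unequal capture, which the documents neither state nor exclude. This part of the objection stands, and the point is conditional because of it.

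Nor can contact practice after the last visit be checked. The supplied protocol postdates the lock, and its survival follow-up section now reads as not applicable. Protocol 5.3 lets the sponsor ask for survival status on every subject, which would be symmetric, but this is optional and belongs to the later revision.

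The stakes are also modest. The standard error of the ipilimumab 3-year estimate with 120 subjects is about 3.6 points, larger than the worst-case loss of 2.7. In a separate run of 1,500 simulated trials the OS hazard ratio moved by less than 0.01, and SAP 7.5 treats the OS p-value as descriptive.

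What does not stand is the suggestion that permitting later alive dates solves the problem. Permission does not oblige anyone to obtain them for every survivor. A systematic loss is also not excused by being smaller than sampling error.

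**Conclusion.** The gap is real and minor. The SAP gives deaths and alive dates no common end date, so Kaplan-Meier estimates beyond 24 months can be biased down if late deaths are captured more completely than late survival. In the worst case the 3-year rate loses 0.7 to 2.7 points for ipilimumab and 0.4 to 1.2 points for DTIC. At a 6-month lag the difference between arms shrinks from 8.1 points (12.5 − 4.4) to 6.6 (9.8 − 3.2). In relative terms DTIC loses slightly more (27% against 22%).

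These figures rest on the SAP's exponential design inputs, an assumed lag of 1 to 6 months, capture of every late death, and no updating of survivors. With equal updating the bias is nil.

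A reader might take this as a threat to the primary result. It is not one: the minimum of 2 years' follow-up puts every death after the cut-off beyond the 24-month estimate.

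**What to change.** In SAP 4.2.2 and 7.5.2, apply one date to both outcomes. Deaths and last-known-alive dates after the data cut-off are censored at the cut-off, survivors' status is confirmed as of that date where the information is already available, and later deaths are listed separately. The alternative is a survival-status sweep of all living subjects, with the sweep date as the end date for deaths and survivors alike.

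Because the database was locked on 03Jun2019, the practical step now is to report OS truncated at the cut-off as a sensitivity analysis, with the number of deaths after it.

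The cost is one sentence in the SAP and one line of derivation. Truncation needs no new data; a sweep would. The downsides are that a few late deaths leave the OS analysis (about 1 to 7 under the assumptions above), and that truncation without confirmed alive status at the cut-off leaves some residual downward bias.

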### **7.5.2.1 Comparison between Treatment Groups**

OS is the key secondary efficacy endpoint. The distribution of OS will be compared between treatment groups using a two-sided log-rank test stratified by M substage (M1a+M1b versus M1c) and BRAF mutation status (yes vs no), as recorded in the IVRS. The HR, and its associated two-sided 80% CI, of ipilimumab to DTIC will be estimated using a Cox proportional hazards model, stratified by the factors described above, and with treatment as the single covariate.

- Comparison of OS

